IV lidocaine is an effective adjunct for perioperative analgesia. Intravenous lidocaine is a nonopioid method of perioperative analgesia.¹⁴⁻¹⁶ It is an amide local anesthetic that works primarily through inhibition of nociceptive stimuli via sodium channel blockade. This is not the primary mode of action when given intravenously. This is because the concentrations achieved with low-dose intravenous administration are similar to systemic absorption with epidural delivery, approximately 1 μ M. These low concentrations would not be sufficient to block any substantial number of sodium channels throughout the body. Intravenous lidocaine likely has local and central actions, including inhibition of noxious stimuli and encouraging the release of endogenous opioids.¹⁷ As a non-opioid analgesic, intravenous lidocaine is effective in reducing pain, opioid consumption, ileus, and hospital length of stay.¹⁸⁻²⁰ Intravenous lidocaine has been studied most extensively in abdominal surgeries.^{18,20-23} Koppert et al found a 35% reduction in morphine equivalent opioid consumption after major abdominal surgery.²⁰ These authors also reported reduced pain complaints with activity, which supports our hypothesis that systemic lidocaine will improve recovery with faster rehabilitation. Similarly, Kuo et al found a 33% reduction in opioid requirements after major abdominal surgery with reduced ileus and a reduced mean length of stay.²² There has been only limited investigation into systemic lidocaine in orthopedic surgery.. Farag et al performed a randomized trial of intravenous lidocaine versus placebo in elective spine surgeries.¹⁹ Subjective pain complaints were less in the lidocaine cohort. It is important to note that nearly 50% of the patients in this study underwent cervical surgeries, distinctly less invasive than thoracolumbar surgery.. Thus, the efficacy of intravenous lidocaine in a population at highest risk for large opioid requirements has not been investigated. Systemic lidocaine has been safe in the studies performed^{21,24}. Serum concentrations of lidocaine at commonly prescribed doses (2mg/kg bolus, 2mg/kg/hr infusion) remain lower than toxic levels.²⁵ Adverse events may include cardiac abnormalities, such as arrhythmias. Studies investigating lidocaine in cardiothoracic surgery, however, have not found evidence of an increased risk of arrhythmia in this high risk population.²⁶⁻²⁸ A systematic

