There are no prior studies investigating the use of intravenous lidocaine for the management of pain associated with adolescent idiopathic scoliosis surgery. As such, the dosage chosen comes from prior work in abdominal surgery and elective spine surgery^{18,19,22}. These studies have shown lidocaine to be effective in improving pain scores, reducing opioid consumption, and improving patient reported outcomes measures. Lidocaine will be given at the induction of anesthesia until 24 hours after arrival to the Post-Anesthesia Care Unit (PACU) or Pediatric Intensive Care Unit (PICU).

A research pharmacist not involved in the care of the patient will deliver lidocaine, 8mg/mL, in D5W (Baxter International, Deerfield, IL, USA), or D5W (Baxter International) to the operating room for continuous infusion. A separate bag containing 1mg/kg of lidocaine in D5W, or an identical volume of plain D5W, will be delivered for bolus delivery. All solutions will be packaged identically, to avoid accidental unblinding. The study pharmacy will report both loading bolus volume and volume/hr rate for the infusion in the electronic medical record. The total volume of study drug/placebo administered will be recorded.

E Study Design

E1 Overview or Design Summary

Anesthesia, other than the lidocaine, will be given as standard of care per physician discretion

Study Drug: After a 1 mg/kg lidocaine bolus with induction, a lidocaine 1 mg/kg (IBW)/hr IV infusion with maximum dose of 200 mg/hr or D5W (placebo) at equal volume rate of administration will begin prior to skin incision and continue intraoperatively for duration of the case. Study drug will be discontinued upon 24 hours of stay in PICU or PACU postoperatively. Study drug will be dosed according to ideal body weight (IBW). Patient height, weight, age, and gender will be delivered to the study pharmacy prior to the day of surgery for calculation of IBW and dosing parameters.

E2 Subject Selection and Withdrawal

Study participants will be AIS patients recruited from Orthopaedic Spine clinics at Center of Advance Medicine Barnes Jewish and St. Louis Children's hospitals. Given the single disease investigated, AIS, we anticipate that our results will be generalizable to AIS patients at other institutions. We will enroll 50 patients, 25 per group, over two years. Approximately 60 AIS surgeries are performed per year at our institution.

2.a Inclusion Criteria

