1. Adolescent idiopathic scoliosis indicated for posterior spinal fusion.
2. Ages between 12 and <18 years of age.
3. Parent/Guardian capable of providing informed consent for study participation.

2.a Exclusion Criteria

1. Age < 12 or > 17.9 years old.

Intravenous Lidocaine to Reduce Postoperative Opioid Consumption and Improve Recovery After Posterior Spinal Fusion for Adolescent Idiopathic Scoliosis

- 2. Unable to obtain consent for the surgical intervention or study, or if mental capacity prohibits the ability to provide consent and complete patient-reported outcomes tools.
- 3. Diagnosis of sepsis or infection
- 4. Diagnosis of primary or metastatic malignancy.
- 5. Participation in another clinical trial.
- 6. Past or current diagnoses of a cardiac arrhythmia or first/second degree heart block.
- 7. Past or current seizure disorders.
- 8. Known allergy to bupivacaine.
- 9. Significant liver disease
- 10. Significant kidney disease
- 11. Known pregnancy
- 12. Known allergy to lidocaine and/or benzocaine
- 13. Planned anterior approaches for treatment of scoliosis deformity.
- 14. Limited English proficiency (e.g. unable to obtain informed consent for surgery without a translator)
- 15. Ward of the State children

2.b Subject Recruitment Plans and Consent Process

Description of Recruitment Process

- 1. Subject selection will be equitable. No patient will be included or excluded on the basis of gender, race, religion, national origin, or sexual orientation. Refusal to participate in the study will not affect the patient's access to care or surgical priority.
- 2. The research coordinator will identify all patients with AIS in the orthopedic clinics. An interview will determine study eligibility.
- 3. Subjects will not be compensated for their participation. There will be no advertisement material. All follow-up care is according to standard of care, with no non-standard tests, imaging, or follow-up appointments.

2.c Randomization Method and Blinding

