The low plasma levels have not been associated with hemodynamic instability nor have they been associated with changes in cardiac contractility. No interactions with the autonomic nervous system have been reported and there are no known effects on sinoatrial conduction. Lidocaine is metabolized by the liver, with less than 10% excreted in urine. Complications are rare. Despite concerns for arrhythmias, intravenous lidocaine has been used in cardiothoracic surgery without increased rates of cardiac complications. Given this volume of evidence, we feel that intravenous lidocaine in the setting of AIS surgery is safe.

3.b Treatment Regimen

After a 1mg/kg IBW lidocaine bolus with induction, a lidocaine 1 mg/kg/hr (IBW) IV infusion with maximum dose of 200 mg/hr or D5W (placebo) at equal volume rate of administration will begin prior to skin incision and continue intraoperatively for duration of the case. Study drug will be discontinued upon 24 hours of stay in either PACU or PICU postoperatively.

Method for Assigning Subjects to Treatment Groups

Patients consenting to randomization will be randomized 1:1 to the control vs study groups. A permuted randomized block approach¹ with blocks of size 4, 6 and 8. Given the relatively large number of patients to be enrolled, no stratification will be performed. After 30 patients are enrolled, an interim analysis, without unblinding, of baseline covariates will be performed to ensure equal distribution between groups. If distribution is uneven for covariates concerning for confounding, then stratification by these covariates will be employed to ensure equal distribution with randomization.

3.c Blinding of Study Drug

This is a Phase IV, randomized, triple-blind, placebo-controlled trial with two study groups: postoperative standard of care with opioid patient controlled analgesia (PCA) and IV lidocaine infusion versus postoperative standard of care plus normal saline placebo. Block randomization into one of the two groups will be based on a random table generated using an R-program. Group 1 (Study) will receive intravenous lidocaine during and after posterior spinal fusion for AIS. Group 2 (Control) will receive saline placebo during and after surgery.

F Study Procedures

F1 Screening for Eligibility

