Both the leukocyte frequencies and leukocyte cell surface phenotype will be measured by flow cytometry. This approach will allow hypothesis-based assessment of pathways demonstrated to contribute to the postoperative immune phenotype, while also providing data for a discovery-driven analysis to define novel mechanisms. Patients will be identified based on inclusion/exclusion criteria as described above. Blood samples with following time points: immediately preoperatively, 4 hours and 8 hours post incision, day 1 post surgery, and day 2-3 post surgery. All blood samples will be collected into 6 ml EDTA-containing vacutainers and three aliquots prepared for fixation by mixing 1.25 ml blood with 1.75 ml Proteomic Stabilizer (Smart Tube, Inc, San Carlos, CA). Following fixation, samples will be stored at -80 °C until flow cytometric analysis. For each patient and time point, one aliquot of the fixed and frozen blood will be used for immunophenotyping. The remaining aliquots will be used for mass cytometry as described and preserved as a "biobank" for potential future studies.

We will analyze signaling events in all major leukocyte subsets and compare phospho-signal median intensities between the different time points and treatment groups to define any immune modulatory effects of lidocaine during surgery.

The primary outcome measure is total, in-hospital opioid consumption following surgery for AIS. Opioid consumption will be measured in morphine-equivalent dosage (MED), to allow for the use of different opioid medications (e.g. fentanyl, hydromorphone, oxycodone) over the course of care.

Secondary outcome measures to assess recovery are the Patient Reported Outcomes Measurement Information System (PROMIS) Mobility (M) and Pain Interference (PI) domains. PROMIS is a general measure of health administered over particular health domains. The SRS-22 will be used in assessing the quality of life in AIS patients. The SRS-22r includes 22 items distributed among five different factors (pain, self-

Intravenous Lidocaine to Reduce Postoperative Opioid Consumption and Improve Recovery After Posterior Spinal Fusion for Adolescent Idiopathic Scoliosis

image/appearance, function/activity, mental health, and satisfaction with management). Each component includes five items, except for the “satisfaction with management”, which only contains two items. Secondary measures to assess the anti-inflammatory effect of lidocaine will be serum levels of IL-10, IL-4 and IL-12.

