Secondary outcome measures to assess recovery are the Patient Reported Outcomes Measurement Information System (PROMIS) Mobility (M) and Pain Interference (PI) domains. PROMIS is a general measure of health administered over particular health domains. This instrument has been tested extensively and is reliable and precise.⁴⁵ Scores range from 0-100 and are normalized so that a score of 50 is the population mean, with 10 points representing a standard deviation is 10 points. For the Mobility domain larger scores represent more function; for the PI domain larger scores represent more pain. The instrument administered via computer-adaptive testing (CAT) to minimize question burden. The Scoliosis Research Society 22 (SRS-22) will be used in assessing the quality of life in AIS patients. The SRS-22r includes 22 items distributed among five different factors (pain, self-image/appearance, function/activity, mental health, and satisfaction with management). Each component includes five items, except for the “satisfaction with management”, which only contains two items. Secondary measures to assess the anti-inflammatory effect of lidocaine will be serum levels of IL-10, IL-4 and IL-12.

The anticipated outcome is decreased in-hospital opioid consumption for those patients treated with intravenous lidocaine. Other anticipated outcomes are decreased opioid consumption at three-months after surgery, with improved recovery as measured by PROMIS-M and PROMIS-PI measures at 6 weeks, 3 months, 6 months, and 12 months after surgery. We anticipate that the anti-inflammatory effect of lidocaine will reflect a smaller postoperative inflammatory response as measured by IL-10, IL-4, and IL-12.

G Statistical Plan

G1 Sample Size Determination and Power

The target sample size of 50 patients, 25 per group, is based upon a two-tail test at the 0.05 level of significance, with 80% power to detect an effect size of $d=0.8$. Prior data from our institution has shown an average postoperative morphine-equivalent consumption of 149 mg with a standard deviation of 37 mg. The proposed effect size is equivalent to approximately a 20% reduction in postoperative morphine-equivalent opioid consumption. The primary outcome measure is the inpatient measure of postoperative opioid consumption. As such, loss-to-followup is not possible, though 25 per group accounts for 10% loss due to treatment noncompliance which is unlikely.

G2 Analysis Plan

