General Analysis Strategy: Our approach to data analysis includes three consecutive stages. Most analyses will be performed using SAS software, which

Intravenous Lidocaine to Reduce Postoperative Opioid Consumption and Improve Recovery After Posterior Spinal Fusion for Adolescent Idiopathic Scoliosis

has a wide range of statistical routines and offers great flexibility in data manipulation.

Descriptive Analysis and Data Reduction:

Quality control will be ongoing throughout the project, as part of data management procedures that monitor data quality at each site and overall. However, prior to analysis, the data will be fully examined to confirm data quality and make final corrections. After addressing data quality, each variable will be summarized via marginal distributions as well as by relevant separate and combined study factors [(e.g., treatment, crossover status, patient demographics (age, gender, race)], and clinical factors (e.g., curve type, curve magnitude, etc.)]. Distribution summaries for continuous variables will include means, medians, interquartile ranges, minima and maxima and standard deviations; those for categorical variables will include proportions and 95% confidence intervals. The amount and patterns of missing data will be examined early and regularly during data collection to detect possible problems with instrument completion. Prior to analysis the amount and patterns of missing data are also important to see whether adjustments will be needed at the Inferential Analysis Stage. Those who complete data collection will be compared with those who drop out before the end of follow-up to identify potential selection biases, causing the study pool to differ from the target population. Transformations will be employed as needed to produce variables that conform to the distributional assumptions underlying the regression models that will be used.

After 10 patients have completed the study, immunophenotyping with flow and mass cytometry will be performed to confirm appropriate data are collected with the chosen panels.

H Data Handling and Record Keeping

H1 Confidentiality and Security

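### G2 never describes its inferential stage: fix one primary model and scale for total in-hospital MED before unblinding, with pre-surgery body weight as covariate (a possible gain, not an established one)

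*Combined protocol and SAP*

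**What the plan says.** - **Outcome (F2):** "The primary outcome measure is total, in-hospital opioid consumption following surgery for AIS". It is measured in MED, with no fixed number of hours, so the sum runs over each patient's own stay. Length of stay is not a listed outcome.
- **Sample size (G1):** the target of 50, 25 per group, "is based upon a two-tail test at the 0.05 level of significance, with 80% power to detect an effect size of" d = 0.8. The inputs are in mg: "Prior data from our institution has shown an average postoperative morphine-equivalent consumption of 149 mg with a standard deviation of 37 mg". G1 names no test and no covariate. It also says that 25 per group already allows for a 10% loss.
- **Analysis (G2):** three consecutive stages are announced. Only the descriptive and data-reduction stage is written. An inferential stage is mentioned once, in connection with missing data, and not described. The only statement about models is "Transformations will be employed as needed to produce variables that conform to the distributional assumptions underlying the regression models that will be used".
- **Analysis sets (F3, I1):** intent-to-treat, as-treated and per-protocol analyses are mentioned without a model.
- **Weight (E1):** "Patient height, weight, age, and gender will be delivered to the study pharmacy prior to the day of surgery", for dosing. The age range (2.a) is "Ages between 12 and <18 years of age".
- **Randomisation (2.c):** unstratified at first, but stratification on unnamed covariates may be introduced after 30 patients.
- **Background (B1):** "intravenous lidocaine is effective in reducing pain, opioid consumption, ileus, and hospital length of stay". B1 adds that most of this work was in abdominal surgery, and D2 says there are no earlier studies in AIS surgery.

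**The concern.** A reader cannot tell from G2 which comparison decides the trial: an unadjusted difference in mg, an adjusted one, or either on a transformed scale. G1 suggests the first and G2's mention of regression suggests something else. Two things follow.

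First, precision may be left unused. The outcome is in mg rather than mg/kg, in patients from 12 up to 18 years, and weight is known before treatment starts. If weight is related to MED, adjusting for it narrows the interval without more patients. Second, if model and scale are not fixed before unblinding, the reported version can be questioned whatever it is.

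A related matter of interpretation is that the outcome is summed to discharge while the background says lidocaine can shorten stay. A lower total could then mean less opioid per hour, fewer hours, or both. The plan has nothing that would separate these.

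**Working it through.** **Inputs from G1:** two-sided alpha 0.05, d = 0.8, SD 37 mg, mean 149 mg, 25 per arm. **Assumed:** R², the share of within-arm MED variance explained by weight (R² = ρ²). The documents do not give it, so a range is shown.

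**1. Reproduce G1.** 0.8 × 37 = 29.6 mg, and 29.6/149 = 19.9%, matching the stated reduction of about 20%. The normal approximation gives n = 2(1.96 + 0.842)²/0.8² = 24.5, so 25 per arm. Power at 25 is 80.7% by that approximation and 79.1% by noncentral t (48 df). G1's figure therefore reproduces with no loss. With a 10% loss, 0.9 × 25 = 22.5 per arm remain.

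**2. ANCOVA power.** Noncentral t with 2n − 3 df and noncentrality [0.8/√(1 − R²)] × √(n/2)/√v. Here v = 1 + t²/(2n − 2) is the penalty for chance imbalance in weight, averaged over t with 2n − 2 df; its mean at n = 25 is 1 + 1/46.

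**3. 95% CI half-width at 25 per arm.** Unadjusted: 2.011 × 37 × √(2/25) = 21.0 mg. Adjusted: 2.012 × 37 × √(2/25) × √[(1 − R²)(1 + 1/46)].

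| Analysis | Power, 25/arm | Power, 23/arm | Power, 22/arm | Half-width, 25/arm |
|---|---|---|---|---|
| Unadjusted | 79.1% | 75.6% | 73.6% | 21.0 mg |
| ANCOVA, R² = 0 | 78.3% | 74.6% | 72.6% | 21.3 mg |
| ANCOVA, ρ = 0.2 (R² = 4%) | 79.9% | 76.3% | 74.3% | 20.9 mg |
| ANCOVA, R² = 10% (ρ = 0.32) | 82.4% | 78.9% | 77.0% | 20.2 mg |
| ANCOVA, R² = 20% (ρ = 0.45) | 86.5% | 83.4% | 81.6% | 19.0 mg |
| ANCOVA, R² = 30% (ρ = 0.55) | 90.6% | 87.9% | 86.4% | 17.8 mg |

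At 25 per arm the adjusted and unadjusted analyses break even at ρ of about 0.15. The largest loss is 79.1 − 78.3 = 0.8 points.

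**4. Cost of an open choice.** I simulated 400,000 trials per cell with no treatment effect, normal MED and 25 per arm. Each analysis alone rejects in 4.9–5.0% of trials. Taking the smaller of the adjusted and unadjusted p-values gives 5.6%, 6.5%, 7.1% and 7.5% at R² = 0, 10%, 20% and 30%. Only one choice is modelled here, so these are illustrations and not bounds: leaving the scale or a rank test open as well would raise them.

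**5. Length of stay.** No size can be given. The documents report neither length of stay nor opioid use by hour.

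**The case against.** The strongest reply is that an unadjusted two-group comparison is valid in a randomised trial, G1 already implies one, and choosing weight is a preference. Much of this stands.

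- **The gain is unproven.** Arm descriptions in 3.c refer to "postoperative standard of care with opioid patient controlled analgesia (PCA) and IV lidocaine infusion". Patients titrate PCA to pain, which may weaken any link with weight. At ρ = 0.2 the gain is under one point. The documents do not rank weight against age or curve magnitude either.
- **Selective reporting.** A reader might infer that the sponsor means to choose the model after seeing results. The documents do not say so. The rates in step 4 show only what prespecification rules out.
- **The outcome.** A reader might infer that total in-hospital MED is a faulty outcome because stay may differ by arm. That does not follow: a shorter stay may be a real benefit, and the evidence for it comes mostly from abdominal surgery.
- **Data.** E1 sends weight to the study pharmacy. It does not say that weight enters the study database, and H1 limits recording to what is necessary, so adding it may not be entirely free.

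What the reply does not meet is that G2 commits to no analysis. A sponsor who prefers another covariate, or none, still has to write down one model and one scale.

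**Conclusion.** The point holds as a worthwhile, low-cost improvement. G2 omits the inferential stage and leaves the primary model, covariates and scale unstated. Weight adjustment is a reasonable way to fill the gap because its downside is under one point of power and its possible gain is larger: about 3, 7 and 11 points at R² of 10%, 20% and 30%. Those gains rest on assumed values of R², on G1's SD of 37 mg, and on 25 evaluable patients per arm. If the 10% loss in G1 means patients without usable data, power is 74–76% unadjusted and 77–79% with R² of 10%, so adjustment of that strength would not restore 80%.

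The documents do not support saying that the gain is likely, that the unadjusted test is wrong, or that the primary outcome is in error. The fixed-window analysis is supportive only.

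**What to change.** Before unblinding, write the inferential stage into G2:

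1. **Primary comparison.** Intention-to-treat ANCOVA of total in-hospital MED, in mg, on treatment with pre-surgery body weight as a linear covariate. Add any covariates used for stratification after patient 30. Report the adjusted difference with its 95% CI, and the unadjusted difference beside it.
2. **Scale.** Keep mg, the scale of G1. Log MED is a sensitivity analysis only. Do not let observed skewness decide the primary scale, since logging changes the effect from a difference to a ratio.
3. **No pilot test of the covariate.** Checking the correlation in historical records would not settle the choice. With an assumed 50 records, an observed r of 0.15 has a 95% CI of about −0.13 to 0.41, and the loss being guarded against is under one point.
4. **Stay.** Keep total in-hospital MED as primary. Add a supportive analysis of MED over one fixed window from PACU/PICU arrival, its length set before unblinding. Report length of stay by arm.

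**Cost:** about a paragraph of text, one supportive analysis, up to about one point of power if weight is unrelated to MED, and possibly a few extraction fields (weight, dose times, length of stay) from medical records that H1 says staff already review.
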